3.3 Study Measures

The following data will be collected from Epic for study purposes:

- Subject demographics (gender, age, race, BMI)
- Hospital admission and discharge dates
- Hospital admission and discharge anti-coagulation medications and fish oil utilization, etc.
- Pre-operative standard of care lab work (CBC, CMP, PT/INR, etc.)
- Type of surgical procedure performed
- Intraoperative hemoglobin/hematocrit (H/H) levels if available
- Post-operative standard of care lab work, days 1 & 2 (CBC, BMP, etc.)
- Number of transfused packed red blood cell units during peri-operative period
- Hemoglobin/hematocrit levels before and after transfusion
- Post-operative DVT prophylaxis
- Length of hospital stay for current hip fracture admission
- Readmission rates within 30 days of hip surgery along with admission diagnosis
- Complications within 90 days of surgery
- Death within 90 days of surgery along with cause of death

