3.4.2 Secondary Study Outcomes

The secondary outcomes of this study include:

- Length of inpatient hospital stay
- Readmission within 30 days post hip surgery along with the associated readmission diagnosis
- Complications within 90 days post hip surgery
- Death within 90 days post hip surgery

4 Study Population and Duration of Participation

Subjects will be recruited from geriatric hip fracture patients acutely admitted through the Lancaster General Hospital Emergency Department and treated by OAL physicians. Consenting subjects will be followed for 90 days post-surgery. Participation ends upon the completion of the 3-month post-operative visit with the OAL provider.

The enrollment phase is projected to take approximately 24 months.

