6.2 Surgical Period

The surgical period includes subject randomization and administration of study drug just prior to surgery. The research subject receives appropriate hip fracture surgical intervention based on their fracture pattern and determination by the treating surgeon.

The CRC will review Epic for peri-operative study data including:

- Lab work: CBC (Complete Blood Count), CMP (Comprehensive Metabolic Panel), PT/INR (prothrombin time and International Normalized Ratio)
- Blood transfusions administered peri-operatively
- Hemoglobin/hematocrit (H/H) levels before and after blood transfusions
- Adverse events

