6.3 Follow Up

6.3.1 Hospital Discharge

The CRC reviews Epic for post-operative study data including:

- Lab work: CBC (Complete Blood Count), CMP (Comprehensive Metabolic Panel), PT/INR (prothrombin time and International normalized ratio)
- Blood transfusions administered post-operatively
- Hemoglobin/hematocrit (H/H) levels before and after post-operative blood transfusions
- Adverse events

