6.3.2 Follow Up Visits

The subject receives routine hip fracture post-operative care per the LGH geriatric fracture program. The post-hospital observational phase will include a minimum of two post-operative follow-up evaluations at two (2) weeks, six (6) weeks, and three (3) months.

The two (2) week, six (6) week, and three (3) month standard of care post hip surgery patient assessment will include evaluation of the following:

- X-rays to evaluate hip fracture and hardware placement
- Dressing check (2 week only)
- Physical therapy progress
- Weight bearing status
- Pain medication management
- Post-operative anti-coagulation management
- Bone density osteoporosis prevention conversation

The CRC conducts a medical chart review at the 6 week and 3 month time points for scheduled and unscheduled office visits a subject has with any provider for the following items:

- Subject assessment by the OAL provider
- Medication changes and updates
- Laboratory tests (if done)
- Hospital readmission and associated diagnosis in the interim since discharge after hip surgery
- Adverse events

If a subject reports visits or hospitalizations outside the LG system, study personnel will request permission to obtain data from the providers or health systems. If a subject is reported to be deceased during the follow-up period, the CRC will record this event in the study database.

6.4 *Unscheduled Visits*

It is anticipated that <5% of subjects require an additional unscheduled visit. Typically additional visits are to evaluate wound healing. Any relevant information from these visits will be captured by the medical chart reviews at 6 weeks and 3 months.

7 *Statistical Plan*

Statistical support will be provided by the Lancaster General Research Institute.

7.1 *Sample Size and Power Determination*

Power calculations are based on the assumptions that 20% of the control group will require transfusion as a result of the hip fracture and surgery, and that use of TXA will reduce that percentage by half to 10%. For 80% power with a two-sided alpha of 0.05, and using a likelihood ratio test, the sample size is calculated to be 200 per group with a 1:1 assignment ratio, or 400 total subjects.

[figure not shown]
7.2 *Statistical Methods*

For assessing the primary endpoint, we will calculate an odds ratio (with a 95% confidence interval) for transfusion with p-values calculated using a likelihood ratio.

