As a secondary outcome, daily hemoglobin and hematocrit levels will be assessed using a mixed-effects linear model with adjustment for appropriate covariates. Safety/complication outcomes such as 30-day readmissions, embolic events or other complications will be assessed using appropriate binary or Poisson models. Descriptive statistics using appropriate comparative models will be used to assess homogeneity of demographics and any differences in outcomes between the control and intervention groups.

One interim analysis is planned to assess the primary endpoint for significant efficacy sufficient to stop the trial early. The interim analysis is planned for the $\frac{3}{4}$ point of the trial or a minimum of 300 subjects enrolled. To compensate for one interim and one final analysis, we will employ the O'Brien-Fleming adjustments to significance level criteria with $p < 0.0054$ for the interim analysis and $p < 0.0492$ for the final analysis. Based upon a simulation of our primary outcome, futility will be reached at the interim analysis point if the control group has a 30 (30/150 = 20%) or fewer subjects that have experienced a transfusion and the intervention group has 26 (26/150 = 17.3%) or more subjects that have experienced a transfusion. Even if the remaining 50 intervention subjects to be enrolled experience no transfusions and the transfusion rate remains at 20% in the control group, H_0 will not be rejected.

Futility Boundary Based Upon Control Group Transfusion Rate and Projected Intervention Group Number Transfused

8 Safety and Event Reporting

The study will comply with requirements of the Lancaster General Human Research Protection Program (HRPP) policies regarding reporting of unanticipated problems and adverse events.

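### Does the hemoglobin analysis in section 7.2 need a written rule for values drawn after a red-cell transfusion?

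*Combined protocol and SAP*

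**What the plan says.** Section 7.2 introduces hemoglobin and hematocrit as a secondary outcome and gives the method in one clause: "daily hemoglobin and hematocrit levels will be assessed using a mixed-effects linear model with adjustment for appropriate covariates". The covariates, the day or days of interest and the handling of transfused subjects are not given there or elsewhere.

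The outcome does not appear in section 3.4.2, whose list opens "The secondary outcomes of this study include" and names length of stay, readmission, complications and death.

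The data collection is fuller than the analysis text. Section 3.3 lists "Post-operative standard of care lab work, days 1 & 2", "Intraoperative hemoglobin/hematocrit (H/H) levels if available", "Hemoglobin/hematocrit levels before and after transfusion" and the number of red-cell units given. Section 6.2 adds "Blood transfusions administered peri-operatively", and section 6.3.1 has the coordinator abstract "levels before and after post-operative blood transfusions".

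The planning rates are in section 7.1: 20% of controls transfused, and an assumption that "use of TXA will reduce that percentage by half to 10" per cent.

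**The concern.** Transfusion raises hemoglobin, and the plan expects twice as many placebo as TXA subjects to receive it. Placebo values drawn after transfusion are therefore propped up more often, and the difference between arms narrows on those days. A reader who takes the hemoglobin result as evidence on blood loss, which sections 1 and 5.4 give as the rationale for the drug, would see too small an effect.

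The unnamed covariates add a second worry. An analyst might enter a subject-level indicator for ever having been transfused. That variable arises after randomization and is itself driven by low hemoglobin, so adjusting for it can distort the comparison further. The same data could then give visibly different estimates depending on a choice made after they are seen.

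**Working it through.** **1. The plan's own figures.** The documents state no figure for the hemoglobin analysis. The 20% and 10% rates used below belong to the sample size, which reproduces. The usual two-proportion formula gives n = [1.960·√(2·0.15·0.85) + 0.842·√(0.20·0.80 + 0.10·0.90)]² / 0.10² = (0.990 + 0.421)² / 0.01 ≈ 199 per group. The likelihood-ratio version gives 197. Exact power of the likelihood ratio test at 200 per group is 81.1%.

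**2. Absolute shrinkage.** On a day when all transfusions have been given, the loss in the arm difference is

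(placebo share transfused − TXA share transfused) × mean rise = (0.20 − 0.10) × rise = 0.10 × rise.

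For assumed rises of 0.5, 1, 1.5 and 2 g/dL this is 0.05, 0.10, 0.15 and 0.20 g/dL. At 20% vs 15% it is half as much, and at equal rates it is zero. Values drawn before any transfusion lose nothing.

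**3. Relative shrinkage, sharp trigger.** The following are assumptions, not in the documents: normal values, SD 1.0–1.5 g/dL, rise 1–2 g/dL, one hemoglobin cut-off shared by both arms (a modelling device, not a clinical rule), and transfusion after the day-1 draw. Then 20% vs 10% implies a true difference of 0.44 SD (1.28 − 0.84), which is 0.44 g/dL at SD 1.0 and 0.66 g/dL at SD 1.5. Day-2 loss is 0.10 × rise divided by that difference. The two-day average loss is half of it, because day 1 is unaffected. Power is from simulation at 200 per arm.

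| SD | Rise | Day-2 loss | Two-day loss | Day-2 power, all values |
|---|---|---|---|---|
| 1.0 | 1 | 0.10/0.44 = 23% | 11% | 97% |
| 1.0 | 2 | 0.20/0.44 = 45–46% | 23% | 78% |
| 1.5 | 1 | 0.10/0.66 = 15% | 8% | 99% |
| 1.5 | 2 | 0.20/0.66 = 30% | 15% | 95% |

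Without any transfusion effect, power is 99%.

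**4. Looser trigger.** Transfusion is rarely decided by hemoglobin alone. With trigger noise equal to the SD, the implied true difference is multiplied by √2, to 0.62–0.93 g/dL. Day-2 loss then runs from 0.10/0.93 = 11% to 0.20/0.62 = 32%.

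**5. A different setup.** This simulation assumes three post-operative draws, a baseline SD of 1.3, an SD of 0.9 for the drop, a within-subject SD of 0.5 and a true effect of 0.72 g/dL. The last-day difference falls to 0.64 (rise 1) or 0.56 (rise 2), a loss of 11% or 22%. Averaged over draws in a mixed model, all values give 0.67 or 0.64, against 0.70 with post-transfusion values set aside. That is a loss of about 0.03 or 0.06 g/dL (4% or 8%). The averages rest on 12 simulated trials (Monte Carlo SE about 0.025), with every method applied to the same data.

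**6. The alternatives.** At SD 1.3 and rise 1.5 the true difference is 0.44 × 1.3 = 0.57 g/dL. With transfusion after the day-1 draw, the day-2 estimates are:

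- all values: 0.57 − 0.15 = 0.42
- ever-transfused covariate: 0.38 (0.24–0.43 depending on coding)
- time-varying post-transfusion term: 0.57
- post-transfusion values set to missing: 0.57
- fixed 1 or 2 g/dL subtracted: 0.52 or 0.62

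If half or all transfusions precede the day-1 draw, the triggering value is not modelled and the correlation with baseline is 0.5, setting values to missing gives only 0.52 or 0.45.

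**The case for a change.** The strongest case for a change is that one dataset can yield anything from about 0.38 to 0.57 g/dL for a named secondary outcome, according to a decision the plan leaves open. Writing the rule before unblinding would cost a few lines and some programming. Excluding post-transfusion values would remove some later values from about 15% of subjects, (20% + 10%)/2.

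Part of this stands. The omission is real, and no other section fills it. The warning against an ever-transfused covariate is sound, although leaving out a variable measured after randomization is ordinary practice and needs no protocol text.

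The rest does not carry. Calling the all-values result too small presupposes a target of hemoglobin without transfused cells. Blood loss is rationale and potential benefit in this plan. It is not an objective in 2.1 or 2.2, nor an outcome in 3.4.1 or 3.4.2. Making that hypothetical quantity the main target, and relying on a missing-at-random model to reach it, is a choice on which reasonable statisticians differ.

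The obvious rule, dropping everything after the first transfusion, also has faults. Unless it is limited to transfusions after study drug, it discards post-operative data because of a baseline event. It removes every scheduled post-operative value from subjects transfused during surgery. It also leaves unclear how an extra draw taken because hemoglobin was low should enter a model indexed by day.

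**Conclusion.** No change to the plan is needed. Keeping all values in the mixed model gives a sound comparison of hemoglobin under routine transfusion care, and that is a natural reading of section 7.2. What is missing is detail that an analyst can supply sensibly. Units given and values before and after transfusion are already collected, so a second, labelled analysis that removes the contribution of transfusion can be reported if blood loss is of interest.

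Read as an effect on blood loss, the all-values estimate is low by at most 0.10 g/dL per 1 g/dL of rise at the planned rates. In relative terms that is roughly 4–23% averaged over post-operative days and about 11–46% on the last day. The upper ends come from one corner of the assumptions (SD 1.0, rise 2, sharp trigger). Only the 20% and 10% come from the documents; spread, rise, timing, correlation and trigger are assumed.

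If TXA reduces transfusion, the shrinkage works against the drug. The primary endpoint is transfusion itself, the sample size rests on it, and the interim efficacy and futility rules in 7.2 use it alone, so none of them is touched. The absence of hemoglobin from 3.4.2 is a listing slip with no effect on the analysis.

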10.2 Data and Safety Monitoring

The Data and Safety Monitoring Committee (DSMC) for TAHFT comprises four individuals who work at LGH. Because the drug is an approved drug and there is significant experience with its use, it is believed that an internal committee can adequately monitor the trial. The committee will include a trauma surgeon, anesthesiologist, orthopedic surgeon, and orthopedic nurse, as well as a biostatistician. In addition, the principal investigator, [name], will attend committee meetings to address protocol. As the principal investigator, he is the person most familiar with the drug protocol and in the best position to address questions about it. However, he will not participate in any votes about study continuation or termination.

The first meeting of the committee will take place once the 50 subjects have been enrolled or after 6 months, whichever occurs first. Thereafter, the committee will meet biannually to review accumulated safety data and as hoc as needed to review or address any adverse events. The principal investigator will be aware of all adverse events that may occur in the study and will be responsible to call ad hoc meetings of the DSMC if necessary. Specific safety outcomes to be monitored include:

- Rate of 30 day readmissions and reason
- Complications within 90 days from surgery
- Other unanticipated events

One interim analysis will be conducted when 75% of enrollment is achieved to determine if the study should stop early for efficacy or futility. It also will allow assessment of the benefits concordantly with the risks.

11 Ethical Considerations

The study will not begin until it has received approval from the LGH Institutional Review Board (IRB). Any changes to the protocol or consent form that represent potential changes to the risk-benefit ratio or an increase in what is required of subjects will be submitted to the IRB as an amendment for review before it is implemented (unless a delay in implementation would compromise subject safety).

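### The O'Brien-Fleming thresholds in section 7.2 fit an interim look at 50% of the data, but the look is planned at 75%

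*Combined protocol and SAP*

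**What the plan says.** Section 7.1 fixes the design: "For 80% power with a two-sided alpha of 0.05, and using a likelihood ratio test". It expects that "20% of the control group will require transfusion as a result of the hip fracture and surgery", with TXA halving this rate to 10%. On size it states that "the sample size is calculated to be 200 per group with a 1:1 assignment ratio, or 400 total subjects".

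Section 7.2 adds one interim efficacy analysis, timed at the three-quarter "point of the trial or a minimum of 300 subjects enrolled". The thresholds are introduced with "To compensate for one interim and one final analysis" and given as "O'Brien-Fleming adjustments to significance level criteria with $p < 0.0054$ for the interim analysis and $p < 0.0492$ for the final analysis". The futility rule in the same section is worked with 150 subjects per arm.

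The Study Summary repeats the three-quarter timing, and section 10.2 agrees: "One interim analysis will be conducted when 75% of enrollment is achieved to determine if the study should stop early for efficacy or futility". No section mentions a look at 50%, a spending function, or a reason for an interim bound stricter than the named method gives.

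**The concern.** The plan specifies a method, a timing and two thresholds, and the three do not agree. An O'Brien-Fleming boundary depends on when the look is taken: the later the look, the less strict the interim criterion and the stricter the final one. The printed pair has the shape for a look half-way through, not at three quarters.

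These are the criteria on which the monitoring committee would recommend stopping for efficacy. If the planned effect is real, the trial is more likely to go on randomising to placebo after the named rule would have stopped it. For some interim results the label and the number give opposite answers, and that should be settled before anyone sees unblinded data. A report describing the boundary as O'Brien-Fleming would also be inaccurate.

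**Working it through.** **Inputs.** Two-sided alpha 0.05, 80% power, likelihood ratio test, 20% versus 10%, 200 per group (section 7.1). One interim and one final analysis, interim at 300 of 400 or 150 per arm, thresholds 0.0054 and 0.0492 (section 7.2). 75% timing confirmed in section 10.2. The information fraction is t = 300/400 = 0.75.

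**Sample size reproduces.** The pooled two-proportion formula gives n = [1.960·√(2·0.15·0.85) + 0.842·√(0.2·0.8 + 0.1·0.9)]² / 0.10² ≈ 199 per group, against the stated 200. Power at 200 per group without an interim look is 0.802 by the normal approximation and 0.811 by exact enumeration of the likelihood ratio test.

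**Timing implied by the stated pair.** An O'Brien-Fleming boundary has z(interim) = C/√t and z(final) = C, so t = (z final / z interim)².
- p = 0.0054 gives z = 2.782; p = 0.0492 gives z = 1.967.
- t = (1.967/2.782)² = 0.50.

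Solved exactly at t = 0.50, the classical pair is 0.0052 / 0.0480. The printed pair is a slightly loose version of this and would spend 0.0513 if used at 50%.

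**The pair for t = 0.75.** The interim and final statistics are treated as bivariate normal with correlation √0.75, and C is solved for overall two-sided 0.05.
- Classical O'Brien-Fleming: C = 2.015, interim z = 2.015/√0.75 = 2.327. Thresholds 0.0200 / 0.0439.
- Lan-DeMets O'Brien-Fleming-type spending, 0.025 per side: z = 2.340 and 2.012. Thresholds 0.0193 / 0.0442.
- Ratio to the stated interim level: 0.0200/0.0054 = 3.7; 0.0193/0.0054 = 3.6.

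**Overall alpha at t = 0.75 (normal theory).**
- Stated pair 0.0054 / 0.0492: 0.0497.
- Only the interim value corrected, 0.0200 / 0.0492: 0.0547. The two values must therefore change together.

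**Operating characteristics.** Exact two-stage enumeration, 20% versus 10%, likelihood ratio test at 150 and then 200 per arm, efficacy stopping only:

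| | 0.0054 / 0.0492 | 0.0200 / 0.0439 |
|---|---|---|
| Stops for efficacy at interim | 36.7% | 55.1% |
| Expected size | 400 − 100·0.367 = 363 | 400 − 100·0.551 = 345 |
| Overall power | 81.2% | 80.5% |

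**In counts.** With 30/150 transfused on control, the printed bound needs 13 or fewer on TXA. The 75% bound needs 15 or fewer. Fourteen (p = 0.0084) or fifteen (p = 0.0145) would cross the named method's boundary but not the printed one.

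**Futility example.** With 40/200 on control at the end, 25/200 on TXA gives p = 0.0413 and 26/200 gives p = 0.0585. Both 0.0492 and 0.0439 lie between these, so the printed futility count of 26 against 30 does not change.

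**The case against.** The strongest defence is that the error is on the safe side. By normal theory the stated pair holds overall alpha below 0.05, and its power is slightly higher than the replacement's. On the scale of patients the two interim bounds differ by two transfusions in the TXA arm when control has 30. That is all correct, and it is why this is a mis-stated stopping rule and not a threat to the validity of a positive result.

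The expected saving of 363 − 345 = 18 subjects also assumes that enrolment halts at exactly 300. The plan does not say recruitment pauses for the look. With 400 subjects over about 24 months, even accrual (an assumption) is about 17 a month, so a month of data preparation would use up much of the saving. The 18 subjects are best read as an upper figure.

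A strict late bound could also be deliberate, to keep more subjects for the complication outcomes. The plan does not say so; it attributes both numbers to O'Brien-Fleming, and both fit the half-way shape. This limits the harm but does not reconcile label, timing and thresholds.

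Finally, the alpha figures are normal-theory values. In exact enumeration with 20% in both arms, the likelihood ratio test rejects slightly more than 5% of the time under either pair (0.0514 stated, 0.0511 replacement). This comes from the test's approximation and does not favour the stated pair.

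**Conclusion.** The concern holds. The printed thresholds are not those O'Brien-Fleming gives for a look at 75%, in either its classical or its Lan-DeMets form. The interim criterion is 0.0054 where the method gives 0.0193 to 0.0200, and the final criterion is 0.0492 where it gives 0.0439 to 0.0442. Under the planned effect this lowers the chance of stopping early for efficacy by about 18 percentage points (55.1% to 36.7%). Type I error is protected and the 80% power target is met.

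The conclusion takes the enrolment fraction as the information fraction. That is reasonable because the primary outcome is acute post-operative transfusion, known within the hospital stay for most subjects. The stopping probabilities and expected sizes assume 20% versus 10%, exactly 150 per arm at the look, and no futility stopping.

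**What to change.** In section 7.2, replace both thresholds with the O'Brien-Fleming values for an information fraction of 0.75: interim p < 0.0200 and final p < 0.0439 (z = 2.327 and 2.015), or the Lan-DeMets pair 0.0193 and 0.0442. Name the version used. Because 300 is stated as a minimum, add that the bounds will be recomputed from the spending function at the fraction actually reached. Do not change the interim value alone.

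If the stricter interim bound is wanted, keep 0.0054, describe it as a fixed conservative bound and remove the O'Brien-Fleming label. The final level could then be as high as 0.0494, although this makes no practical difference to power.

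Recheck the futility boundary figure against the new final level; the printed example of 30 and 26 stands.

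The cost is a sentence or two in section 7.2 and about 0.7 percentage points of power (81.2% to 80.5%). The maximum sample size is unchanged.
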